STUDY PROTOCOL Social Behavioral Template

Piloting a novel social support intervention for addiction recovery

Protocol Number

2000035434

Protocol Version

7/23/24

10

Clinical Trials Registration Number: NCT# NCT06022107

Confidentiality Statement:

Synopsis

Purpose

The purpose of this study is to pilot a novel web-based intervention to help people who engage in hazardous drinking cut down or quit drinking. This intervention will be implemented through Qualtrics, where each night, participants (referred to as "support-receivers") will access a Qualtrics link containing brief written and video encouragement and information generated by people in addiction recovery communities ("support-providers"). The intervention is designed to help the user maintain motivation to not drink in the short-run, and build connections with addiction recovery communities to sustain their recovery in the long-run.

Objectives

This study will first determine feasibility and acceptability of inviting addiction recovery communities to be support-providers and creating content for this intervention. Second, it will determine feasibility and acceptability of individuals who engage in hazardous drinking using this intervention (aka support-receivers), and determine preliminary efficacy of this intervention on alcohol use and engagement in recovery support services. Third, it will correlate characteristics of content created by support-providers with support-receivers' ratings of the content to identify which characteristics are well-received by support-receivers, to guide future content creation.

Study Population

The target support-providers are individuals who are involved in addiction recovery community (e.g., support group meeting facilitators, volunteers at recovery community centers) or are allies of the addiction recovery community. The target support-receivers are adults who engage in hazardous drinking and live in Connecticut.

Number of Participants

We will recruit up to 50 support-providers, and up to 30 support-receivers to use the intervention. This sample size is appropriate for a pilot study. We will recruit a subset of these participants (10 support-providers and 10 support-receivers) to participate in a follow-up qualitative interview.

Study Design

This is a study to develop and test an intervention that comprises three parts: 1) We will invite individuals (support-providers) to provide video and written content for the intervention. 2) We will recruit participants who engage in hazardous drinking to be support-receivers and use the online intervention daily for a month; they will also fill in questionnaires about their substance use and engagement with recovery support services at the beginning and end of the study to determine preliminary efficacy. 3) We will then administer qualitative interviews to both support-providers and support-receivers to gain insight into intervention's feasibility and acceptability, and to identify ways to improve the intervention.

Study Duration

It will take support-providers about 30 minutes to complete their portion of this study. Support-receivers will complete questionnaires prior to using the intervention (no longer than 1 hour to complete), then use the intervention for a few minutes each night for one month, and then complete follow-up questionnaires (no longer than 30 minutes to complete) at end of intervention use and one month after the end of intervention use. Both support-providers and support-receivers can take part in an optional qualitative interview after, which will take no more than 30 minutes. Data collection will likely last 1-2 years.

Outcome Variables

We will collect data on recruitment and attrition rates of support-providers and support-receivers to determine feasibility. To determine acceptability, we will collect quantitative data on how often support-receivers engaged with the intervention throughout the month, and qualitative data to obtain participants' views and experiences of the intervention, including barriers and facilitators of use. Preliminary efficacy will be assessed using questionnaire measures of substance use and engagement in recovery support services administered at the start and end of the intervention. We will also characterize the video content created by support-providers and correlate them with support-receivers' ratings of the content, to identify which characteristics are well-received by support-receivers, to guide future content creation.

Locations/Facilities

	7.5	Data Analysis Tools	24
	7.6	Data Monitoring	24
	7.7	Handling of Missing Data	24
8	Data	a/Specimen Handling and Record Keeping	25
	8.1	Subject Data Confidentiality	25
	8.2	Data Quality Assurance	26
	8.3	Data or Specimen Storage/Security	26
	8.4	Study Records	26
	8.5	Access to Source	26
	86	Retention of Records	26

APPROVED BY THE YALE UNIVERSITY IRB 8/9/2024

Protocol Number 2000035434

7/23/24 v10

	8.7	Data and Safety Monitoring Plan	27
9	S	tudy Considerations	28
	9.1	Institutional Review Board (IRB) Review	28
	9.2	Research Personnel Training	28
	9.3	Study Monitoring	28
	9.4	Unanticipated Problems and Protocol Deviations	29
	9.5	Study Discontinuation	30
	9.6	Study Completion	30
	9.7	Conflict of Interest Management Plan	30
	9.8	Funding Source	31
	9.9	Publication Plan	31
1()	Appendices	32
1 ·	1	List of Tables	33

Protocol Revision History

Version Date	Summary of Substantial Changes
V2 6/30/23	As per IRB feedback, SPs are no longer considered human subjects in this study, and all such references have been removed.
V3 7/14/23	In order to be able to analyze the videos from SPs, SPs will be considered human subjects.
V4 11/27/23	Included study phone as an option for conducting visit 1 remotely, changed a questionnaire to short-form version, rearranged when participants would do which questionnaire, included NCT#.
V5 1/2/24	SPs no longer will be compensated for recording videos. Additional questionnaire added for SR to complete at 3 time points. SRs will be given the option to receive a progress report at the end of the study.
V6 1/23/24	Included measures to screen out scammers posing as potential SR participants, option to provide people who do not meet eligibility criteria with a resource sheet, expanding SR recruitment to CT more broadly
V7 1/25/24	Additional measure added to screen out scammers: potential SR participant will be asked to show some form of ID during the zoom visit to verify their identity. This ID will be visually verified by the study team during the zoom visit and will not be recorded or saved.
V8 1/31/24	Disclaimer to be included during Zoom visit 1 with SRs to state that LDART is not an established form of addiction treatment and if emergencies arise during the study to seek medical care and/or contact 911. Option for SRs to leave comments on videos. Additional analyses to be performed on SP videos and SR rating data.
V9 2/22/24	In-person recruitment method added.
V10 7/23/24	SP compensation increased, SP video collection re-opened.

1 Background

1.1 Background

The impact of addiction on societies worldwide has been devastating and costly¹. Existing pharmacological² and psychological^{3,4} interventions can be efficacious, but their efficacy is sometimes negated if deficits in social determinants of health are not concurrently addressed⁵⁻⁷. Indeed, studies have found that social support, especially recovery-oriented support networks, is a consistent predictor of addiction recovery⁸⁻¹². This is particularly true during the first few months of recovery, where relapse rates range from 20-85%^{13,14}. Connecting individuals in early recovery to resources in the addiction recovery community (ARC), such as support group meetings and recovery community centers, is thus crucial for sustaining addiction recovery¹⁵⁻¹⁷.

Despite its importance, accruing social support can be a difficult process for at least two reasons. First, finding and accessing recovery support services can be challenging due to individual factors (e.g., lack of motivation, anxiety about meeting strangers) and structural factors (e.g., lack of comprehensive lists of recovery resources). Second, because this process is time- and effort-consuming, it requires one to prioritize the long-term benefits of recovery over the short-term benefits of substance use^{18,19} -- an ability that is often compromised in individuals with substance use disorders²⁰. Thus it is important to keep individuals motivated during this process, for example by having immediate, salient rewards when one reaches their recovery goals. These two barriers can be overcome using a combination of community reinforcement approach²¹ and contingency management²², respectively. Although this is a highly effective treatment approach²³, few clinicians are trained in the former, few treatment centers implement the latter²⁴, and both require individuals to be already engaged in formal treatment in order to gain access to these specialized treatments.

We propose a novel social support intervention that circumvents all of these barriers, tentatively called *Let's Do Addiction Recovery Together* (*LDART*). Individuals in early recovery will receive a short prerecorded video every night for a month, contingent on them meeting their recovery goal for the day (e.g., not drinking, attending a support group meeting). These videos, generated by members of the local ARC, have two purposes: 1) to congratulate and motivate the recoveree on their recovery journey (in an acutely rewarding way, not unlike monetary rewards in contingency management); 2) to introduce and "put a face and a voice" to local recovery support services, thereby reducing informational and psychological barriers to engagement. If the daily recovery goal is not met, they will receive written words of encouragement and information on a recovery support service, albeit in a less engaging and rewarding format. Given that many in early recovery feel socially isolated²⁵, we hypothesize that these videos will be a potent social reward and motivator for reaching one's recovery goals, such as reducing substance use and increasing social support.

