2.1 Rationale and Study Significance

As mentioned above, getting individuals in early recovery from hazardous alcohol use to stay motivated in their recovery can be challenging for a number of reasons, and effective ways of doing this (e.g., contingency management, community reinforcement approach) are often difficult to access. There is thus a need for low cost and easily accessible interventions to keep individuals motivated throughout their recovery. This pilot study will assess feasibility, acceptability, and preliminary efficacy of a novel social support intervention that remotely delivers social reinforcements (vis-à-vis videos of support from the ARC) contingent on reaching individualized recovery goals to individuals in early recovery from alcohol use. The long-term goal of this intervention, if proven to be successful, is to be a freely available resource that can run in an automated manner (with the exception of video inspection to ensure appropriate quality and content), and scaled both spatially (videos can be obtained from people beyond state lines) and temporally (with more videos, this intervention can go on for more than one month, thereby further sustaining recovery).

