3.1 Purpose

This pilot study will assess feasibility, acceptability, and preliminary efficacy of a novel social support intervention (LDART) that remotely delivers social reinforcements contingent on reaching individualized recovery goals to individuals in early recovery from hazardous alcohol use. The long-term goal of this intervention, if proven to be successful, is to be a freely available resource that can run in a mostly-automated manner, and scaled both spatially and temporally, that may improve alcohol use and quality of life outcomes for individuals who engage in hazardous drinking.

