SRs will then receive a reminder email on the day they decide to begin the intervention (SR Day 0 email; Intervention Materials), and will receive their first Qualtrics link via email on the night they decide to start participating in the intervention (Intervention Materials), each night for a month (Intervention Materials). In these links, they will answer whether they met their recovery goal for the day. If they answer yes, a celebratory message from a SP will be shown; if no, an encouraging message from the SP will be shown. Participants will rate on a scale of 0-5 how motivating and supportive they found the message to be with the option of leaving written feedback on the video. Information provided by the SP about the details of the recovery support service they're affiliated with will also be displayed. SRs will then select their recovery goal for the next day (e.g., stay sober, go to a support group meeting). This entire process should take less than 5 minutes to complete each night. They will be compensated a maximum of \$30 during this month, depending on how frequently they engage with the intervention; this will be paid as a lump sum at the end of the intervention. On the last day of the intervention, they will complete a few additional questionnaires on the Qualtrics link (Intervention Materials). This should take less than 30 minutes to complete, and they will be compensated \$30 for their time. They will also be emailed a Qualtrics link with questionnaires one month after the completion of the intervention (SR questionnaires), which should take about 30 minutes to complete, and they will be compensated \$30. In the last questionnaire, SRs will be asked whether they would like to receive a progress report of their time during the study (SR progress report).

Gather feedback (SRs and SPs): Participants who indicate that they can be contacted regarding an optional 30-minute qualitative interview will be emailed after they upload their video (for SPs), and after they complete their 1-month post-intervention questionnaire (for SRs). Participants who consent to being contacted and do not complete their portion of their study may also be contacted, to better understand barriers to completion. This interview will revolve around feedback on, feasibility and acceptability of the intervention, how to improve it, and possible names for the intervention (*QI discussion guide*) for \$20.

SP Flow Diagram

Protocol Number 2000035434

7/23/24 v10

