6.1 Study Procedures

SP protocol: After consent is complete, they will click on a Qualtrics link (*SP video-recording link*) to record two short videos to motivate someone to keep reaching their daily recovery goal. This Qualtrics link will work on smartphones such that the SP can record and upload videos directly from their smartphone. If used on a computer, the SP will have to record the video using software such as Photo Booth on Mac or Windows Camera on PC, and then upload the video as a file to Qualtrics. SPs will also be asked to optionally provide information on the recovery work they do (e.g., facilitate a support group meeting on Wednesdays at 6pm) and how to access it (e.g., provide the zoom link or physical address of the recovery community center), and a brief demographic questionnaire. Finally, they will be asked under what circumstances the study team can contact them.

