SR pilot intervention: Upon completion of the pre-screening form, a zoom meeting or phone call will be scheduled with a member of the study team for Visit 1. Participants will first be asked the same questions that they filled in in the eligibility screen to see if their answers match up. This is to verify the authenticity of the potential participant. This visit will first introduce the study intervention to the participant, with the disclaimer that the intervention is not an established form of treatment and that if emergencies arise while participating in the study, to seek treatment or call 911. Then, a member of the study team will go over the consent document if they are interested in participating, getting informed consent via REDCap, and filling in questionnaires about their demographics, substance use, and recovery capital (SR Questionnaires). Their preference for what time to receive emails/text reminders to log onto LDART each night will be recorded. The visit should last no longer than an hour, and participants will be compensated with a \$30 electronic gift card for their time. SRs will then receive an email to a Qualtrics link on the night they want to begin the intervention (SR Day 0, Intervention Materials). On the days immediately before and after using the intervention (i.e., Day 1 and Day 28), participants will complete the Timeline Follow Back for alcohol use and recovery services, which is built into the Qualtrics intervention. Each night for a month, they will open the Qualtrics link to answer to indicate whether they met their recovery goal for the day. If they answer yes, a celebratory message from a SP will be shown; if no, an encouraging message from a SP will be shown. Video messages will be shown on some nights and written ones (i.e., transcription of the video) on others. Participants will rate how motivating and supportive they found the message to be with the option of leaving written feedback on the video. Information provided by the SP about the details of their recovery support service will also be displayed. They will then select their recovery goal for the next day (e.g., stay sober, go to a support group meeting). This entire process should take less than 5 minutes to complete each night. They will be compensated a maximum of \$30 during this time, depending on how frequently they engage with the intervention; this will be paid as a lump sum at the end of the intervention.

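### Section 6.1 does not tie video to the daily goal as 1.1 and 2.1 do, and the rating analysis in 7.2 separates neither transcript nights nor goal status

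*Combined protocol and SAP*

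**What the plan says.** Two descriptions of the nightly content stand in the current protocol.

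The background and rationale make the video the reward. Section 1.1 states that SRs "will receive a short prerecorded video every night for a month, contingent on them meeting their recovery goal for the day". For other nights it says "If the daily recovery goal is not met, they will receive written words of encouragement and information on a recovery support service", and it calls that format less engaging and less rewarding. Section 2.1 says the pilot assesses "social reinforcements (vis-à-vis videos of support from the ARC) contingent on reaching individualized recovery goals". Section 3.1 keeps the contingency but names no format: the intervention "remotely delivers social reinforcements contingent on reaching individualized recovery goals".

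The operative sections attach the contingency to the type of message. Section 4 says "If they answer yes, a celebratory message from a SP will be shown; if no, an encouraging message from the SP will be shown", and 6.1 has the same yes/no rule. Section 6.1 then adds, as a separate sentence: "Video messages will be shown on some nights and written ones (i.e., transcription of the video) on others". No rule for which nights is given, and 6.2 (assignment) is marked not applicable. The synopsis describes nightly links "containing brief written and video encouragement and information generated by people in addiction recovery communities" and states no contingency.

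In both 4 and 6.1 the SR rates the message shown, whatever its format. Section 7.2 correlates these ratings with content, audio and visual features of the support-provider (SP) videos. It does not mention transcript nights, goal status or repeated ratings by the same SR in that analysis.

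**The concern.** In a pilot, the definition of the intervention is a main product. A reader of this protocol cannot tell whether an SR who missed the goal could still be shown a video, or whether one who met it could be shown only a transcript.

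The same gap reaches the analysis that is meant to guide future content, which 3.3 lists among the secondary objectives. An SR who reads a transcript cannot hear pitch variability or see eye contact, so a rating from that night carries no information on those features. And because message type follows the goal answer under 4 and 6.1, a content feature more common in celebratory messages is rated mostly on days when the SR succeeded. A plain correlation may then credit the message with the SR's good day.

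**Working it through.** **The nightly rule, side by side**

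| Night | Section 1.1 | Sections 4 and 6.1 as written |
|---|---|---|
| Goal met | Video | Celebratory message, video or transcript |
| Goal not met | Written words | Encouraging message, video or transcript |

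Section 1.1 allows two combinations of goal and format; 6.1 as worded allows four. The 1.1 rule is a special case of the 6.1 wording (celebratory video if met, encouraging transcript if not), so the texts are not strictly incompatible. What is missing is a statement that this special case is the one used. The SP instructions do not settle it: 6.1 asks each SP to "record two short videos to motivate someone to keep reaching their daily recovery goal", without assigning either video to met or unmet nights.

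**What the rule changes**

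- Primary outcomes (4.2.1): recruitment, attrition, engagement, drinking and recovery capital. None uses message format, so none is computed differently.
- Rating analysis (7.2): affected in two ways. The plan gives no figure to reproduce here, so the sizes below rest on stated assumptions.

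**Dilution of audio and visual features**

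Assume a feature has correlation r with ratings on video nights and none on transcript nights, is unrelated to format, and the rating variance is similar on both. With a share p of rated nights on video, the pooled covariance is p times the video-night covariance, so the pooled correlation is about p × r.

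- Assumed r = 0.24.
- Under the 1.1 rule p is the share of goal-met nights; assumed 0.6: 0.6 × 0.24 = 0.144.
- Under a format rule unrelated to the goal, assumed p = 0.5: 0.5 × 0.24 = 0.12.

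A simulation of 30 SRs over 28 nights agreed, with pooled values of about 0.14 and 0.12.

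**Spurious association for content features**

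Take a content feature with no effect on ratings whose mean differs by d standard deviations between celebratory and encouraging messages. Let ratings be g points higher on goal-met nights. Assume a goal-met share of 0.6, between-SR SD 0.7 and residual SD 1. Then √(0.6 × 0.4) = 0.490, and:

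- r(rating, goal) = 0.490g / √(0.7² + 1² + 0.24g²) = 0.100, 0.197, 0.372 for g = 0.25, 0.5, 1.0.
- r(feature, goal) = 0.490d / √(1 + 0.24d²) = 0.238, 0.440 for d = 0.5, 1.
- Spurious correlation = product of the two:

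| g (points, 0–5 scale) | d = 0.5 | d = 1 |
|---|---|---|
| 0.25 | 0.100 × 0.238 = 0.02 | 0.100 × 0.440 = 0.04 |
| 0.5 | 0.197 × 0.238 = 0.05 | 0.197 × 0.440 = 0.09 |
| 1.0 | 0.372 × 0.238 = 0.09 | 0.372 × 0.440 = 0.16 |

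In the same simulation, within goal-met nights the correlation was about 0.00 in every case. This confounding arises through message type, so it is present under either format rule.

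**What a model can and cannot separate**

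Under the 1.1 rule the indicators for video and for goal met are identical every night, so both cannot enter one model. On video nights alone both are constant, and goal status cannot confound the audio and visual analyses there. If format is unrelated to the goal, goal status still varies among video nights and has to be accounted for.

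**The case against.** The strongest reply is that every sentence in 6.1 can be true under the 1.1 rule. Video would then appear on some nights and text on others, and a transcript is itself a set of written words in a less engaging form. The nightly screens are in the Intervention Materials, which are not part of this document and may state the rule. This stands as far as it goes: the defect is an unstated rule, and the case against the consistent reading rests on 6.1 giving format separately, after both message types.

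It can also be said that 7.2 already refers to ratings of videos, which may imply that transcript nights are excluded. Perhaps so, but 4 and 6.1 collect ratings for every message, and 7.2 gives no exclusion.

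Three stronger inferences are tempting and are not supported.

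- A reader might infer that 3.1 conflicts with 6.1. It does not: it names no video, and a celebratory message given only for a met goal is still contingent.
- A reader might infer that the discrepancy is what prevents the trial from testing contingent video reinforcement. This is a single-arm pre-post pilot and cannot isolate the contingency under either rule.
- A reader might infer a biased comparison of video with text. No such comparison is planned, and any bias calculated for it under the 1.1 rule simply returns the goal-day effect that was assumed.

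**Conclusion.** The point holds as an undefined delivery rule. Sections 1.1 and 2.1 make video the reward for a met goal, while 4 and 6.1 link only message type to the goal and leave format without a rule. The passages need reconciling; which rule is right is for the study team.

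The statistical consequence is confined to the secondary rating analysis. Under the assumptions shown, pooling transcript nights reduces an audio or visual correlation in proportion to the video share (0.24 to 0.12–0.14). Ignoring goal status can give a content feature with no effect a correlation of 0.02 to 0.16. The documents supply none of the effect sizes, so these figures show direction and order of magnitude only. If SRs rate no higher on goal-met days, or if content features do not differ by message type, the second problem disappears.

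**What to change.** 1. State one nightly display rule and make 1.1, 2.1, 4 and 6.1 agree with it. Section 3.1 can stay as it is.
2. For each SR and night, record goal status, message type and the format actually shown. The goal answer is already collected; the protocol does not say that message type and format are stored.
3. In 7.2, relate audio and visual features only to ratings from nights when the video was shown.
4. Analyse ratings with a random SR effect, and either include goal status or work within message type. Add format as a separate term only if the reconciled rule lets format vary independently of the goal.

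Cost: a wording amendment, a check that the two further variables are stored, and slightly more analysis work. Audio and visual features will have fewer ratings. Of at most 30 × 28 = 840, video shares of 0.5 and 0.6 leave 420 and 504. The ratings removed carry no information on those features: ignoring clustering, r√n is 0.24 × √504 = 5.4 on video nights against 0.144 × √840 = 4.2 pooled.
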